VT (mL/Kg IBW)		Brain injury	Passive	< 4	≥ 4 and < 5	≥ 5 and ≤ 8	> 8 and ≤ 10	> 10
VT (mL/Kg IBW)		Chronic hypercapnia	Passive or active	< 4	≥ 4 and < 5	≥ 5 and ≤ 10	> 10 and ≤ 12	> 12
Pmax (cm H2O)		None	Passive	NA	< 10	≥ 10 and ≤ 25	> 25 and ≤ 30	> 30
Pmax (cm H2O)	15, 27, 35	ARDS	Passive	NA	< 10	≥ 10 and ≤ 30	> 30 and ≤ 35	> 35
Pmax (cm H2O)		None or ARDS	Active	NA	< 10	≥ 10 and ≤ 25	> 25 and ≤ 30	> 30
Pmax (cm H2O)		Brain injury	Passive or active	NA	< 10	≥ 10 and ≤ 25	> 25 and ≤ 30	> 30
Pmax (cm H2O)		Chronic hypercapnia	Passive or active	NA	< 10	≥ 10 and ≤ 30	> 30 and ≤ 35	> 35
Pmax-PEEP (cm H2O)	4,	ARDS	Passive	NA	NA	<15	≥15 and <18	≥ 18
RR (b/min)		None	Active	< 10	≥ 10 and < 12	≥ 12 and ≤ 30	> 30 and ≤ 35	> 35
RR (b/min)		Brain injury or ARDS	Active	< 10	≥ 10 and < 12	≥ 12 and ≤ 35	> 35 and ≤ 40	> 40
RR (b/min)		Chronic hypercapnia	Active	< 8	≥ 8 and < 10	≥ 10 and ≤ 35	> 35 and ≤ 40	> 40

Efficacy and safety endpoints are co-primary endpoints:

Efficacy will be calculated as the percentage of time spent with all variables in the optimal target ranges.

Safety will be calculated as the percentage of time spent with at least one variable in the sub-optimal target ranges.

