3.2.2 Secondary endpoints

Secondary endpoints will be recorded continuously until the end of intervention period (up to 28 days after enrolment).

Efficacy

Physiologic parameters:

- Respiratory mechanics (Compliance, resistance, expiratory time constant) will be assessed automatically breath-by-breath.
- Oxygenation (PaO₂/FiO₂, FiO₂, PEEP)
- Ventilation (VT, RR, mechanical power will be assessed automatically breath-bybreath, ΔP , P_{PLAT} , will be assessed twice a day).
- FiO₂ levels to be assessed in both study arms

Outcomes:

• Duration of invasive mechanical ventilation: time between intubation and last extubation or death. When a subject is re-intubated within 48 hours after extubation, the period between extubation and re-intubation is considered as invasive ventilation days.

- Duration of non-invasive mechanical ventilation: noninvasive ventilation refers to CPAP or pressure support NIV delivered before intubation or after extubation. High flow therapy is not considered in this calculation.
- Total duration of mechanical ventilation: sum of duration of invasive and noninvasive mechanical ventilation.
- Time from intubation to first successful Spontaneous Breathing Trial (SBT)
- Passive ventilation duration: passive ventilation is defined when the percentage of subject's triggered breath is lower than 25% of total respiratory rate.
- Weaning duration: time between the first sedation cessation to the last extubation or the last disconnection from the ventilator for tracheostomized subjects. Subjects re-intubated within 48h after extubation will be kept in the study. Subject re-intubated beyond 48h will be considered as weaned from the ventilation.
- VFD to day28 are defined as: the number of days from the time of initiating unassisted breathing to day 28 after start of ventilation, assuming survival for at least 48 hours and no re-intubation within 48 hours after initiating unassisted breathing and continued unassisted breathing to day 28.

NIV will be considered as assisted breathing. CPAP will not be considered as assisted breathing. Ventilator free days will be calculated separately for invasive ventilation support and any other ventilation support (invasive and noninvasive).

If a subject returns to assisted breathing (re-intubated within 48 hours) and subsequently achieves unassisted breathing to day 28, VFDs will be counted from the end of the last period of assisted breathing to day 28.

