3.3 Study Design

EASIVENT is a Pivotal, two-arm, controlled, single-blind, multicenter, randomized trial of INTELLiVENT-ASV versus non automated Ventilation in adult ICU subjects.

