3.4.1 Group sequential design with 2 interim analyses

The planned sample size is a minimum of 254 and a maximum of 508 subjects.

The sample sizes for this trial are calculated using the following assumptions:

- significance level equal to 0.025 (1-sided)
- power of 0.8 (at final analysis)
- allocation ratio of 1:1
- Two interim analyses at half and three-quarter information time (i.e. when half and three-quarter of the subjects are evaluable for response), using spending functions with O'Brien-Fleming-Type boundaries for efficacy and futility.
- Efficacy endpoint (%All in optimal, more is better) on logit-scale:
 - Mean conventional = -1.86
 - Mean INTELLiVENT-ASV = -1.28
 - \circ Sd = 1.5 for both devices
- Safety endpoint (%Any in sub-optimal, less is better) on logit-scale:
 - Mean conventional = -0.09
 - Mean INTELLiVENT-ASV = -0.74
 - \circ Sd = 1.6 for both devices
- Correlation between endpoints = -0.85
- Dropout could occur when subjects are ventilated for less than 24 hours after inclusion because of unexpected death, transfer to another ICU or withdrawal of informed consent. A maximum dropout rate of 5% of these cases is expected. Given the large uncertainty on the assumed performance differences and the inclusion of a sample size reassessment, the initial sample size is not increased to deal with this dropout rate. At the second interim the sample size will be re-estimated, taking this observed dropout rate into account.

The table below shows the sample sizes and characteristics of a study with 2 interim analyses, with O'Brien-Flemming boundaries for efficacy and futility. The final sample size for this group sequential design is 254. 254 stands for the number of subjects with evaluable endpoints and means more subjects might have to be enrolled to reach this number. The p-values for significance are increasing at each analysis while the p-value to stop for futility decreases from the first interim analysis to the final analysis. The study has a high probability to stop at the first interim analysis if both ventilation modes have an equal performance.

Sample sizes and operational characteristics for the trial using O'Brien Fleming boundaries for futility and efficacy.

Analysis	SS	Z	Nominal p	α Spend	end Power	
		Efficacy	Efficacy		(Prob stop H _A)	
1 (IA1)	128	2.96	0.0015	0.0015	0.25	

2 (IA2)	192	2.36	0.0093	0.0097	0.
3 (final)	254	2.02	0.0220	0.0250	0
Analysis	SS	Z	Nominal p	Prob Futility Stop	
		Futility	Futility	(Prob stop under H ₀)	

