Data will be expressed by mean±SD or median (interquartile range) depending on the normality of the distribution assessed with Kolmogorov-Smirnov test. Comparisons will use the two sample Z-test on log-transformed primary endpoint variables. P values <0.025 (one-sided) will be considered significant. Bonferroni adjustment will be applied when applicable. Data will be analyzed using SAS (Version 9.4 or higher).

The tables will be created by treatment arm. Listings with individual values will be provided for all data presented in the tables.

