7.2 Secondary Efficacy Variable

Secondary efficacy variables covering physiologic parameters, clinical outcomes, workload, safety events, typical clinical complications up to day 28 after enrolment and associated interventions will be assessed.

Please refer to section 3.2.2 of SAP for the complete list for the secondary efficacy endpoints.

Data will be expressed by median (interquartile range) or mean±SD and 95% confidence interval depending on the normality of the distribution assessed with Kolmogorov-Smirnov test. Between group differences will be performed using the 2 sample Z-test for normal variables or Mann-Whitney test for variables with a non-normal distribution. If applicable, a Bonferroni correction will be applied for pairwise comparisons corresponding to the sponsor's variable of interest.

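### Two conditional Bonferroni sentences in the SAP name no family, divisor or variables, so no pre-specified rule controls type I error over about 31 tested secondary efficacy variables

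*SAP*

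**What the plan says.** SAP 7.2 covers the secondary efficacy variables listed in SAP 3.2.2. On testing it says: "Between group differences will be performed using the 2 sample Z-test for normal variables or Mann-Whitney test" for the non-normal ones. Its multiplicity rule is one sentence: "If applicable, a Bonferroni correction will be applied for pairwise comparisons corresponding to the" variable that interests the sponsor. The section gives no significance threshold and no sidedness, and it does not say which variable is of interest.

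SAP 4 (General Analysis Definitions) has a second sentence of the same kind. After describing the Z-test on the primary endpoint variables, it says: "P values <0.025 (one-sided) will be considered significant. Bonferroni adjustment will be applied when applicable".

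SAP 3.3 describes a "two-arm, controlled, single-blind, multicenter, randomized trial". Protocol 10.4.5 says: "Efficacy and safety endpoints are co-primary endpoints". SAP 7.1 and 8.2 each set one-sided 0.025 for their own co-primary. SAP 7.3 and 8.4 do the same for the tertiary variables and mention no adjustment.

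Neither document gives an order of testing, a gate on the co-primary result, or a divisor for the secondary tests. Protocol section 10 has no multiplicity rule for them.

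**The concern.** A multiplicity rule has to fix, before unblinding, which tests form the family and what level each receives. Neither Bonferroni sentence does this, and there are two ways to read the one in 7.2:

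- **Pairwise means pairs of arms.** With two arms there is one pair per variable, so the correction divides by one and changes nothing.
- **Pairwise means treatment comparisons on variables the sponsor selects.** The divisor may then exceed one, but the selection is unnamed. It can be made after the results are known, and so can the decision that a correction is applicable.

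Silence might be acceptable if 7.2 labelled the tests descriptive. It does not, and the SAP does so elsewhere: section 6 disclaims inference for the US/EU baseline tests, and 7.5 calls the subset analyses exploratory and supportive. The protocol synopsis presents the trial as the main basis for a pre-market approval application. A ventilator-free-days, ventilation-duration or workload result described there as significant would have no defined error rate behind it.

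**Working it through.** **1. The plan's own figure.** Inputs from SAP 3.4.1:

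- one-sided 0.025, power 0.80, 1:1 allocation
- efficacy difference −1.28 − (−1.86) = 0.58, SD 1.5
- safety difference −0.09 − (−0.74) = 0.65, SD 1.6
- correlation −0.85, which is 0.85 once both endpoints point towards benefit
- looks at 128, 192 and 254; efficacy Z 2.96, 2.36, 2.02; futility Z 0.44, 1.34, 2.02

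Fixed-design totals for 80% power are 210 (efficacy) and 192 (safety). The three-look design was simulated with success requiring both endpoints to cross the efficacy bound at the same look, and futility if either falls below its bound. The probability of success at N = 254 is 0.800 (0.831 without futility stopping). Type I error for one endpoint without futility stopping is 0.0246. So 254 and 0.80 reproduce when both endpoints are required and each uses the full boundary with no alpha split.

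**2. Number of secondary efficacy variables (SAP 3.2.2).**

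- Physiologic, 4 bullets. The first reads "Respiratory mechanics (Compliance, resistance, expiratory time constant) will be assessed automatically breath-by-breath" and holds 3 variables. Oxygenation adds 3 and ventilation 5. The fourth bullet repeats FiO2. Total 11.
- Outcomes, 7 bullets. Ventilator-free days are calculated in two versions. Total 8.
- Associated interventions, 7 bullets. Four drug classes × (duration, dose) = 8, plus 3. Total 11.
- Workload, 1 bullet. Total 1.

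Bullets: 4 + 7 + 7 + 1 = 19. Variables: 11 + 8 + 11 + 1 = 31. Section 7.2 also mentions safety events and typical complications, which are not counted here.

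**3. What the 7.2 correction does, read as pairs of arms.** Number of pairs = 2 × 1 / 2 = 1, so the level is 0.025 / 1 = 0.025. For comparison, Bonferroni over all variables would give 0.025 / 31 = 0.00081, and over the bullets 0.025 / 19 = 0.0013.

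**4. Family-wise error if each test is read at one-sided 0.025 and every null is true.**

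Independent tests: 1 − 0.975^k.

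- k = 31: 0.544; expected false positives 31 × 0.025 = 0.775
- k = 19: 0.382; expected false positives 19 × 0.025 = 0.475

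Equally correlated normal test statistics with correlation ρ and c = 1.96: 1 − ∫ φ(x) Φ((c − √ρ x)/√(1 − ρ))^k dx.

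| assumed ρ | k = 31 | k = 19 |
|---|---|---|
| 0 | 0.544 | 0.382 |
| 0.3 | 0.356 | 0.272 |
| 0.5 | 0.259 | 0.205 |
| 0.8 | 0.129 | 0.110 |

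The documents give no correlations among the secondaries, so ρ is an assumption. The independence figure is a ceiling only for non-negatively correlated tests. The bound under any dependence is the sum, 0.775 for k = 31.

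**5. Repeated looks.** The table list in SAP 10.1 marks the secondary efficacy tables, ITT and mITT, for both interims. One variable read at 0.025 at all three looks has an error of about 0.049. Step 4 does not include this.

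**The case against.** Several points on the other side stand.

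- A reader might infer that the 7.2 sentence is the only multiplicity rule. It is not: SAP 4 has the second one. That sentence is too vague to control error, but it must be counted.
- A reader might conclude that the 7.2 correction certainly does nothing. That is one reading. The closing words on the sponsor's variable of interest allow a correction over selected variables, and on that reading the fault is the open selection.
- A reader might say that 7.2 declares each secondary significant at one-sided 0.025. It does not. The threshold is in SAP 4, directly after a sentence on the primary test; 7.2 gives summaries, a 95% CI and tests. No direction of benefit is stated for variables such as resistance or PEEP, so a one-sided reading is itself an assumption.
- A reader might infer that the SAP 4 sentence halves the level for the co-primaries and costs power. The documents do not support this: SAP 7.1 and 8.2 each keep 0.025, and the stated power reproduces without a split.
- The 54% is an independence figure, and many of these variables are linked by construction. Total ventilation duration is the sum of two others, ventilator-free days appear twice, and each drug class contributes both duration and dose. The correlated range is the fairer guide.
- No passage says that a secondary result will support a confirmatory claim, or that the interims carry a secondary decision rule.

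None of this supplies the missing family, divisor or variables. On either reading of 7.2, the plan followed as written leaves the secondary error rate undefined.

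**Conclusion.** The concern holds in this form: the SAP's two conditional Bonferroni sentences do not control type I error over the secondary efficacy variables, and 7.2 does not withdraw them from inference. If each of about 31 variables is read at the general one-sided 0.025 level and all nulls are true, the chance of at least one false positive is about 54% under independence (38% counting 19 bullets) and about 13% to 36% under assumed equal correlations of 0.8 to 0.3. All of these are well above 0.025. They rest on the variable count, on borrowing the threshold from SAP 4, and on assumed correlations. The primary analysis is not affected. The change should be made, because the rule as stated does not do its job and a standard replacement is cheap.

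**What to change.** Replace both Bonferroni sentences with the following:

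1. Both co-primaries must be met, each at its own boundary, with no alpha split between them.
2. Before the next unblinded look, the sponsor names a short fixed sequence of key secondaries, stating which ventilator-free-days version is meant. The sequence is tested only if both co-primaries are met. The text states the sidedness and the level, for example the nominal efficacy level in SAP 3.4.1 for the look at which the trial stops (0.0015, 0.0093 or 0.0220). The choice and order of variables are the sponsor's.
3. All other secondary results, and the tertiary results, are reported as estimates with 95% CI and no significance wording. This also means removing the 0.025 sentences in SAP 7.3 and 8.4.

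The change is to SAP wording only and needs no new data or subjects. The downside is that fewer secondary and tertiary results can be called significant.

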7.3 Tertiary Efficacy Variable

The tertiary efficacy endpoint is a composite endpoint and will be used to assess the ability to keep ventilation and oxygenation variables in optimal target ranges. The tertiary efficacy variable will be calculated as the percentage of time spent with **ALL** six variables in the optimal target ranges during the ventilation period **from day 8 up to day 28** after randomization:

- 1) Tidal volume (VT)
- 2) Maximum pressure (Pmax)
- 3) Oxygen saturation measured by pulse oximetry (SpO₂)
- 4) End-tidal partial pressure of carbon dioxide (PetCO₂)

- 5) Respiratory rate (RR) for spontaneous breathing subjects
- 6) Pmax-PEEP for passive ARDS subjects

The optimal and sub-optimal ranges are defined by pertinent guidelines for different clinical conditions including normal lungs, brain injury, ARDS, and chronic hypercapnia.

The tertiary efficacy variable will be expressed by median (interquartile range). Log transformation will be performed on the data before performing the 2 sample Z-test. Comparisons will use the 2 sample Z-test for log transformed variables. The P values <0.025 (one-sided, the hypothesis is that INTELLiVENT-ASV is better than conventional non-automated ventilation in terms of efficacy) will be considered significant.

7.4 Sensitivity Analyses

The Primary efficacy analysis will be repeated for the MITT population as sensitivity analysis. Other sensitivity analyses may be performed as appropriate. The Sensitivity analysis will be performed under MAR (Missing at Random) assumption. The Tipping point approach will be implemented to test the MAR assumption.

To check the sensitivity of the results of the primary efficacy analysis to the MAR assumption, MI based on models compatible with Missing Not At Random (MNAR) missingness mechanisms will be used. The approach below, using SAS PROC MI, will be considered:

The "shift imputation" approach: for missing values at a particular visit, it will be assumed that their expected value is smaller (shifted) by a specified amount than for the observed responses (implying that the missing values are more likely corresponding to smaller differences between arms than the observed ones). Different values of the shift will be explored to investigate the sensitivity of the results. This approach can be applied to data with arbitrary missing data patterns.

As other sensitivity analysis, the primary efficacy variable will be analyzed using an ANCOVA model, adjusting for region. All sensitivity analyses will be done at final analysis.

7.5 Subset Analyses

The trial is not sized to test for the presence of treatment by subset interactions. Thus, true treatment by subset interactions will likely be missed, unless they are quite substantial. Conversely, should any particular subset of subjects seem to benefit more or less from therapy than the total population, this will not be taken as evidence of a true treatment by subset interaction, given the likelihood that such an observation could be due to chance alone.

With these caveats in mind, exploratory subset analyses on the primary efficacy endpoint will be performed to identify any major effect. The subgroups have been defined in Section 4.4.

If applicable, the homogeneity testing of the treatment effect across subgroups with the significance level of 0.15 will be performed.

These analyses will be considered as supportive efficacy analyses and conducted without any alpha-level adjustment.

7.6 Individual patient profiles

An individual patient profile plot showing average FiO2, VTe/IBW, Ftot, Fspont, mechanical power and Pmax minus PEEP over all breaths for each 24hours period from day 0 to day 7 will be presented by treatment arms.

8. Safety Evaluation

8.1 Extent of Exposure to Investigational Device

The number of subjects randomized to INTELLIVENT-ASV who switched to non-INTELLIVENT ASV mode will be shown. In addition, for those patients, the total time spent in both modes will be described. Details of all subjects randomized to ASV but transiently ventilated in another mode will be provided in a listing.

8.2 Primary Safety Variable

The primary safety variable will be calculated as the percentage of time spent with **at least one** of the six variables in the sub-optimal target ranges during the **7 days** after randomization:

- 1) Tidal volume (VT)
- 2) Maximum pressure (Pmax)
- 3) Oxygen saturation measured by pulse oximetry (SpO₂)
- 4) End-tidal partial pressure of carbon dioxide (PetCO₂)
- 5) Respiratory rate (RR) for spontaneous breathing subjects
- 6) Pmax-PEEP for passive ARDS subjects

The primary safety variable will be expressed by median (interquartile range). Log transformation will be performed on the data before performing the 2 sample Z-test. Comparisons will use the 2 sample Z-test for log transformed variables. The P values <0.025 (one-sided, the hypothesis is that INTELLiVENT-ASV is better than conventional non-automated ventilation in terms of efficacy) will be considered significant.

Primary safety variable will be performed on the safety population.

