10.4.4 Safety Analysis Population

The Safety population will include all subjects who once received invasive (mechanical or non-mechanical) ventilation. Subjects will be analyzed according to the treatment that they actually received. The safety population will be used for safety analyses.

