3.4.2 Adaptive sample size increase

An adaptive sample size reassessment is foreseen at the second interim analysis. In case promising results are obtained at this interim analysis, additional resources will be committed to the trial. Following Mehta and Pocock (Mehta, 2011), sample sizes will only be increased in case the interim results are promising, in which case the overall type-I error is not inflated by use of the conventional Wald Statistic. The maximum number of additional subjects will be capped at 254 (above the pre-planned 254 subjects) or a maximal total sample size of 508. More specifically, this 'promising zone' is defined in terms of the conditional probability of rejecting the null hypothesis at final analysis, given the estimated performance difference at interim ('conditional power') and assuming that this estimated performance difference is the true underlying difference. Depending on the conditional power (CP) for each of the two endpoints at the second interim analysis, three different zones and anticipated actions are to be considered:

1) **Unfavourable zone**: At least one endpoint with CP < 0.33.

The interim results are so disappointing that it is not worth to increase the sample size to retrieve CP and the original sample size is retained. This zone is defined as 0 to 0.33, for a sample size reassessment at 0.75 information fraction. If the CP for either of endpoints is below 0.33, this is considered unfavourable, and no sample size increase will be performed.

Promising zone: Both endpoints with CP >0.33, at least one endpoint with CP <0.80

If the CP is above 0.33 but below the originally planned 0.80 for at least one primary endpoint, the sample size will be increased by just the right amount to recover the targeted power of 0.80, while not exceeding the pre-specified maximal sample size of 508 subjects. As stated above, both endpoints would need to have a CP above 0.33 and one endpoint a CP below 0.80 to embark on a sample size increase. The sample size increase will be set to the highest of two recalculated sample sizes if both endpoints have a CP between 0.33 and 0.80.

3) Favourable zone: Both endpoints CP >0.80

The conditional power at second interim analysis is 0.80 or larger for both endpoints. In this zone, the interim results are sufficiently favourable that the trial continues to the original sample size without the need to adaptively increase the trial size.

4. General Analysis Definitions

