4.3.1 Intention-To-Treat (ITT) Population

The Intention-To-Treat population (ITT) will consist of all randomized subjects. Subjects who receive the wrong ventilation support will be analysed in the arm to which they were randomized. The ITT population will be used for primary, secondary, and tertiary efficacy analyses.

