4.3.3 Safety Analysis Population

The Safety population will include all subjects who once received invasive mechanical ventilation. Subjects will be analyzed according to the ventilation mode that they received. The safety population will be used for safety analyses.

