Physiology admission scores SAPS II, APACHE II and SOFA, Mechanical ventilation characteristics (INTELLiVENT-ASV, VC, PAC, VAC, SIMV, BiPaP, APRV, PS, ASV, Others) and Arterial Blood Gas analysis (PH, PaO₂, PaCO₂, HCO₃⁻, SaO₂, FiO₂, End-Tidal CO₂) at baseline will be summarized by treatment arms. Similarly, stratification information based on subject condition at inclusion will be tabulated by treatment arm if applicable. In addition, baseline characteristics will be presented by region (US vs EU). For categorical baseline variables, Fisher exact test will be used to test if there's a significant difference between US and EU whereas for continuous variables Mann-Whitney U test will be used to test for differences between the two populations. Results for these statistical tests will be mainly for informative purpose and no inference is intended to be made on these results.

7. Efficacy Evaluation

Efficacy evaluation will be performed on the ITT population. Values for optimal, acceptable, and sub-optimal ranges (maybe different for passive and spontaneous breathing ventilation periods) are listed in Values for optimal, acceptable and sub-optimal ranges of the study protocol.

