8.4 Tertiary Safety Variable

The tertiary safety variable will be calculated as the percentage of time spent with **at least one** of the six variables in the sub-optimal target ranges during ventilation period **from day 8 up to day 28** after randomization:

- 1) Tidal volume (VT)
- 2) Maximum pressure (Pmax)
- 3) Oxygen saturation measured by pulse oximetry (SpO₂)
- 4) End-tidal partial pressure of carbon dioxide (PetCO₂)
- 5) Respiratory rate (RR) for spontaneous breathing subjects
- 6) Pmax-PEEP for passive ARDS subjects

The tertiary safety variable will be expressed by median (interquartile range). Log transformation will be performed on the data before performing the 2 sample Z-test. Comparisons will use the 2 sample Z-test for log transformed variables. The P values <0.025 (one-sided, the hypothesis is that INTELLiVENT-ASV is better than conventional non-automated ventilation in terms of efficacy) will be considered significant.

Tertiary safety variable will be performed on the safety population.

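### The co-primary safety endpoint is tested for superiority by ventilation mode received, with no rule for mixed-mode patients and no analysis by randomised arm

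*SAP*

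**What the plan says.** Protocol 10.4.5 states that "Efficacy and safety endpoints are co-primary endpoints" and gives the hypothesis that the device is better on both. SAP 8.2 tests the safety endpoint on a transformed scale with a two-sample Z-test, one-sided at 0.025, and adds "Primary safety variable will be performed on the safety population".

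That population is defined in SAP 4.3.3: "Subjects will be analyzed according to the ventilation mode that they received". Protocol 10.4.4 agrees: "Subjects will be analyzed according to the treatment that they actually received". SAP 8.4 repeats the choice for days 8-28: "Tertiary safety variable will be performed on the safety population".

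Efficacy is handled differently. SAP 7 says "Efficacy evaluation will be performed on the ITT population", and SAP 4.3.1 says "Subjects who receive the wrong ventilation support will be analysed in the arm to which they were randomized". The MITT, shift/tipping-point and region-adjusted ANCOVA analyses in SAP 7.4 are for primary efficacy only. In SAP 10.1 and 10.2 the primary safety outputs (Table 14.03.03 and Figure 14.03.01) are listed for the safety population alone.

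The safety endpoint also drives the sample-size re-estimation. SAP 3.4.2 sets the zones "Depending on the conditional power (CP) for each of the two endpoints at the second interim analysis" but names no population for the safety calculation.

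**The concern.** Grouping by treatment received is the usual choice for adverse-event tables. This endpoint is a confirmatory superiority claim, and an as-received comparison of it is not a randomised comparison.

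Mixed-mode patients are expected. Protocol 3.4 lets the attending physician return to conventional ventilation at any time. Protocol 8.3.1 allows the device mode to be switched off for procedures. SAP 8.1 plans to count device patients who switched and to describe their time in each mode. Neither document says which group such a patient joins in the safety population. Controls may not cross over (Protocol 8.3.1), so any regrouping would run mainly from device to control. If the patients who leave the device mode do worse and are counted as control, the bias favours the device. If they stay in the device group, the result is close to ITT. The missing rule decides which applies.

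Protocol 8.3.1 also says that patients needing rescue therapy are analysed by intention to treat. It names no endpoint and is not reconciled with SAP 8.2.

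**Working it through.** **1. Is the safety test confirmatory?** The inputs are from SAP 3.4.1:
- efficacy difference 0.58 (-1.28 against -1.86), SD 1.5
- safety difference 0.65 (-0.09 against -0.74), SD 1.6
- correlation -0.85, which is 0.85 when both endpoints are scored towards benefit
- looks at 128/192/254; efficacy Z 2.96/2.36/2.02; futility Z 0.44/1.34/2.02

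The drifts are 0.58/(1.5·√(4/254)) = 3.081 and 0.65/(1.6·√(4/254)) = 3.237. Simulating the three looks (1,000,000 paths) gives these results:
- Safety alone stops for success with probability 0.254/0.424/0.193 by look, matching the plan's 0.25/0.43/0.19.
- Power is 0.836 for efficacy alone, 0.871 for safety alone and 0.800 for both.

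The plan's power of 0.80 is therefore the power to win on both endpoints, and safety is a full part of the confirmatory claim.

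**2. What could regrouping do?** The documents give no switch rate, so these are assumptions: a fraction *q* of 127 device patients is regrouped as control, their mean is *d* worse than the device-arm average, and there is no true safety effect. The test is the final look alone at Z = 2.02 (error 0.0217), with SD 1.6.

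*Case 1: values imputed from the control model*, the natural reading of SAP 4.8 for patients under 80% recorded for non-technical reasons.
- As received: bias = q·d/(1−q); SE = 1.6·√[1/(127(1−q)) + 1/(127(1+q))]
- ITT: bias = q·d; SE = 1.6·√(2/127) = 0.2008

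*Case 2: observed values moved to control*, for example if any conventional ventilation counted as control. This can reach patients with at least 24 h and at least 80% recorded in the allocated mode, whose datasets are complete.
- Bias = 2q·d/(1−q²), with the as-received SE above

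Worked example, q = 0.05 and d = 1 SD = 1.6, case 2: bias = 0.16/0.9975 = 0.160; SE = 0.201; error = 1 − Φ(2.02 − 0.798) = 0.111. The spurious difference of 0.16 is a quarter of the planned 0.65.

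| q | d | Case 1 as received | Case 1 ITT | Case 2 as received | Observed values, randomised arm |
|---|---|---|---|---|---|
| 5% | 0.5 SD | 0.0351 | 0.0343 | 0.0525 | 0.0217 |
| 5% | 1 SD | 0.0547 | 0.0524 | 0.1108 | 0.0217 |
| 10% | 0.5 SD | 0.0571 | 0.0524 | 0.1114 | 0.0217 |
| 10% | 1 SD | 0.1273 | 0.1106 | 0.3379 | 0.0217 |

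In case 1 the grouping itself adds 0.1-0.2 points at q = 5% and 0.5-1.7 points at q = 10%. The rest is missing-data bias, which remains under ITT.

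**3. Sensitivity of these figures** (rows in the table's order).
- If *worse* is measured against non-switchers, case 2 becomes 0.0504, 0.1035, 0.0969, 0.2815.
- With both interims and binding futility, case 1 as received is 0.035, 0.055, 0.057, 0.124 (ITT 0.035, 0.052, 0.052, 0.108), and case 2 is 0.052, 0.109, 0.109, 0.325.
- On the log scale of SAP 8.2 (logit-normal data, 6 or 13 switchers), case 2 is 0.046, 0.078, 0.095, 0.250. The comparator by randomised arm is 0.025, 0.025, 0.025, 0.034, above nominal because the null is set on the logit scale.

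**4. Trial level.** With no effect on either endpoint, joint false success at the final look is 0.011 without regrouping and at most 0.022 with it, because the ITT efficacy test must also be won.

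**The case against.** The strongest reply is that few patients may be regrouped and that the large figures need an unlikely rule. Counting any conventional ventilation as control would turn a routine procedure into a cross-over. The opposite rule, under which any device exposure counts as device, reproduces ITT for these patients. Under a majority-time rule, patients with at least 80% in the allocated mode stay in the device group, and case 2 largely disappears. Protocol 8.3.1 also limits real switching: data collection ends when the investigator takes a patient off study, accidental switches are reversed, and procedural switches are temporary. Finally, the trial-level risk is confined to a true efficacy effect with no safety effect, for two endpoints planned to correlate at -0.85.

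All of this stands as a limit on size. It does not supply the missing rule, because none of these rules is written in the plan. The 80% criterion defines a complete dataset and MITT membership, not group assignment. The one sensitivity analysis that covers both co-primaries treats as missing the patients under 80% recorded for technical reasons (Protocol 10.5, SAP 4.1.1 and 4.8), so it does not address grouping. It is also fair to say that the confirmatory argument does not reach the tertiary variable, and that the extra sensitivity analyses are optional.

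**Conclusion.** The point holds. A confirmatory superiority endpoint is analysed only by mode received, its grouping rule is undefined for patients in both modes, and no analysis by randomised arm is planned for it. Neither the size nor the direction of any bias can be derived from the documents. They depend on the switch rate, on how *received* is later defined and on how SAP 4.8 is applied. Under the assumptions above, the effect of grouping on the error of the safety test runs from negligible (0.1 points, imputed values, q = 5%) to large (34% against 2.2%, observed values moved, q = 10%, 1 SD worse). False success for the trial as a whole rises above 2.2% only if efficacy is truly better and safety is not. The case for change rests on how cheaply the exposure is removed, not on a demonstrated large bias.

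**What to change.** - In SAP 8.2, make the ITT population by randomised arm the primary analysis of the safety co-primary, at the interims and the final analysis. Do the same in SAP 8.4 for consistency.
- Name that population in SAP 3.4.2 for the safety conditional power, and add the matching ITT rows to SAP 10.1 and 10.2.
- Keep the as-received population for adverse-event tables and as a supportive analysis. Define *received* for mixed-mode patients in SAP 4.3.3 before any unblinded analysis, for example by the larger share of recorded time.
- Reconcile the intention-to-treat sentence in Protocol 8.3.1 with SAP 8.2, and align Protocol 10.4.4.
- State in SAP 4.8 whether the recorded values of patients under 80% for non-technical reasons are used or imputed. ITT grouping alone does not remove that part of the bias.
- Optionally, extend the SAP 7.4 sensitivity analyses to the safety co-primary.

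The cost is minor SAP and table-shell work on recordings already collected. The target of 254 evaluable patients and the planned joint power of 0.80 are unchanged. Changing the protocol wording needs an amendment with approvals under Protocol 11.9. SAP 4.9 already records one departure from the protocol, so the population change could be documented there if an amendment is not wanted.
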